14.3 Progression-Free Survival

Progression-Free Survival (PFS) time is defined as the time (in weeks) from first administration of trial treatment until the first date of PD or death due to any cause within 84 days (12 weeks) of last tumor assessment if death occurred during the treatment period, or within 168 days (24 weeks) of last tumor assessment if death occurred during the follow-up period.

PFS will be censored in the following scenarios:

- Participants who do not experience an event (PD or death) will be right-censored on the date of the last evaluable (non-missing and non "Not Evaluable") tumor assessment.
- Participants who start new anti-cancer treatment prior to an event will be censored on the date of the last evaluable (non-missing and non "Not Evaluable") tumor assessment before anti-cancer therapy is given.
- Participants with an event after two or more subsequent missing response assessments (i.e. 2 times the scheduled time interval between two subsequent response assessments) will be censored on the date of the last evaluable (non-missing and non "Not Evaluable") tumor assessment.
- Note: 2 times the scheduled time interval means 84 days during the treatment period and 168 days during the follow-up period (for participants who ended the treatment not for progression)
- Participants who do not have a baseline tumor assessment or who do not have any postbaseline tumor assessments will be censored on the date of first dose unless death occurred on or before the time of the second planned tumor assessment in which case the death will be considered an event.

PFS = (date of PD or death/censoring - date of the first dose + 1)/30.4375 (months).

PFS event / censoring are defined in Table 3:

Table 3 Progression-free Survival Event / Censoring

PFS Event Stat	PFS Event Status		Date of event / censoring
Progressed or died Within two subsequent scheduled tumor assessments after last response assessment of CR, PR or SD		Event	Minimum (Date of PD, Date of death)
	Otherwise	Censored	Date of last tumor assessment with outcome CR, PR or SD or date of first dose, whatever is later
Neither progressed nor died		Censored	Date of last tumor assessment with outcome CR, PR or SD or date of first dose, whatever is later

CR = complete response; PD = progressive disease; PFS= progression-free survival; PR = partial response; SD = stable disease.

The analysis of PFS will be performed according to the RECIST 1.1 per Investigator. For dose expansion participants, analysis of PFS according to RECIST 1.1 as measured by the IRC will also be performed.

The analysis of PFS time will be performed with a Kaplan-Meier method with the same approach as for DR described in Section 14.2. Kaplan-Meier estimates (product-limit estimates) will be presented together with a summary of associated statistics including corresponding two-sided 95% CIs. PFS rates with their CI at 3, 6, 9, 12, 18, 24, 36, and 48 months will be presented, as well as the number of participants at risk and failed.

Listing of PFS will be provided with the following information: dose level/cohort, participant identifier, age, sex, MSI status, PD-L1 expression, date of first administration, date of last tumor assessment, date of event/censoring, event/censoring reason, time to event.

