Measure	Day -28 to First Treatment	D1	D2	D8	D15	D22	D29	D43	D43-50	D57	D71	D85	Until Progression	Discontinuation/ Last Treatment	(+/- 2 weeks) after Last Treatment	Every 12 weeks (+/- 2 weeks)
Written informed consent	X					X										
Inclusion/exclusion criteria	X	X														
Medical history	X															
Cancer disease history	X															
Prior anticancer drug/radiotherapy/ procedures	X															
Other prior medications	X															
Demographic data	X															
HBV, HCV, and HIV testing	X															
Ophthalmology examination including slit lamp evaluation inclusive of the anterior segment and with visual acuity	X															
Physical examination ^{t,x}	X	X	X	X	X	X	X	X		X	X	X	6-weekly ^u	x/X	X	

Table 1	Schedul	e of	Asse	ssme	ents:	Dos	e Es	calati	ion Pa	rt						
	Screening Assessments						Т	Discontinuation/ End-of- Treatment Visits ^w	Safety Follow-up Visit ^w	Long-Term Follow-up ^b						
		V1	V2	V3	V4	V5	V6	V7	V7	V8	V9	V10		Up to 7/28 Days (+/- 5 days) after		
	Day -28 to	W1 D1	W1 D2	W2 D8	W3 D15	W4 D22	W5	W7 D43	W7 D43-50	W9 D57	W11	W13 D85		Decision of Discontinuation/	10 Weeks (+/- 2 weeks)	
Measure	First Treatment	DI	D2	ръ	D15	DZZ	D29	D43	D43-50	ופע	D71	ספת	Until Progression	Last Treatment	after Last Treatment	Every 12 weeks (+/- 2 weeks)
Dermatological assessment ^e	X				X		X	X		X	X	X	6-weekly up to/including Week 25, then every 12 weeks	x/X	X	
SpO ₂	X	X			X		X	X		X	X	X	2-weekly	X	X	
12 lead ECG ^f	X	X/X	X	X	X/X		X	X				X	6-weekly normal ECGs ^u	-/X	X	
Vital signs including weight and height (height at screening only) ^g	X	X	X	X	X	X	X	X	X	X	X	X	2-weekly	x/X	X	
ECOG PSh	X	X	X	X	X		X	X		X	X	X	2-weekly	x/X	X	
Enrollment (if eligible)i	X															
Hematology/ hemostaseology ^j	X	X	X	X	X	X	X	X		X	X	X	2-weekly	x/X	X	
Core serum chemistry ^k		X	X	X		X	X			X	X		2-weekly			
Full serum chemistryk	X				X			X				X	6-weekly	x/X	X	
Serum electrophoresis	X											X		-/X		
Urinalysis ^l	X				X			X				X	6-weekly ^u	x/X	X	
β-HCG pregnancy test (if applicable) ^m	X	X					X			X		X	4-weekly	-/X	X	
FSH (if applicable)	X															

Table 1	Schedul	e of	Asse	ssme	ents:	Dos	se Es	calat	ion Pai	rt						
	Screening Assessments						_		ent Part days) ^a					Discontinuation/ End-of- Treatment Visits ^w	Safety Follow-up Visit ^w	Long-Term Follow-up ^b
		V1	V2	V3	V4	V5	V6	V7	V7	V8	V9	V10		Up to 7/28 Days		
		W1	W1	W2	W3	W4	W5	W 7	W 7	W9	W11	W13	1	(+/- 5 days) after Decision of	10 Weeks	

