	Day -28 to	D1	D2	D8	D15	D22	D29	D43	D43-50	D57	D71	D85]	Discontinuation/	(+/- 2 weeks)	
Measure	First Treatment												Until Progression	Last Treatment	after Last Treatment	Every 12 weeks (+/- 2 weeks)
Tumor evaluation/ staging (CT Scan/MRI/ other) ^{b, n, o, v}	X							Х				X	6-weekly	-/X		X _p
Documentation of AEsw	X	X	X	X	X	X	X	X	X	X	X	X	2-weekly	x/X ^w	Xw	
Documentation of concomitant medications, and procedures	X	X	X	X	X	X	X	Х	X	X	X	X	2-weekly	x/X	Х	X
ACTH, ANA, and RF	X															
Free T4 and TSH	X				X			X				X	6-weekly	-/X	X	
PK sampling										See	Table	3				
ADA sampling										See	Table	3				
Soluble factors										See	Table	3				
TGFβ										See	Table	3				
Tumor tissue or archived surgical specimen (optional)										See	Table	3				
CCI						_				CC						
CCI	C															
Pretreatment and IMP administration ^q		X			X		X	X		X	X	X	2-weekly			

Table 1	Schedul	e of .	Asse	ssme	ents:	Dos	e Es	calat	ion Pa	rt						
	Screening Assessments								ent Part days) ^a					Discontinuation/ End-of- Treatment Visits ^w	Safety Follow-up Visit ^w	Long-Term Follow-up ^b
		V1	V2	V3	V4	V5	V6	V7	V7	V8	V9	V10		Up to 7/28 Days		
		W1	W1	W2	W3	W4	W5	W 7	W7	W9	W11	W13		(+/- 5 days) after Decision of	10 Weeks	
	Day -28 to	D 1	D2	D8	D15	D22	D29	D43	D43-50	D57	D71	D85		Discontinuation/	(+/- 2 weeks)	
Measure	First Treatment												Until Progression	Last Treatment	after Last Treatment	Every 12 weeks (+/- 2 weeks)
Hospitalization on first 2 doses ^r		X			X											
DLT assessment ^s		X	X	X	X	X										
Survival follow-up																X

ACTH=adrenocorticotropic hormone; ADA=anti-drug antibody; AE=adverse events; ANA=antinuclear antibody; β -HCG= β -human chorionic gonadotropin; CT=computer tomography; DLT=dose-limiting toxicity; ECG=electrocardiogram; ECOG PS=Eastern Cooperative Oncology Group Performance Status; FSH=follicle stimulating hormone; HBV=hepatitis B virus; HCV=hepatitis C virus; HIV=human immunodeficiency virus; IMP=investigational medicinal product; MRI=magnetic resonance imaging; PD=progressive disease; PK=pharmacokinetics; RF=rheumatoid factor; SpO₂=Oxygen saturation; TGF β =transforming growth factor beta; TSH=thyroid stimulating hormone, T4=thyroxine.

Unless stated otherwise in a footnote, all procedures and samples should occur prior to trial drug administration.

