- n Tumor evaluations during Screening must be performed within 28 days prior to Cycle 1 Day 1 in order to document the baseline status of the tumor disease using RECIST 1.1 target and nontarget lesions. The subsequent tumor evaluations have a time window of 5 days prior to dosing (-5 days). In case a tumor response according to RECIST 1.1 is documented during the course of the trial, confirmation of the response should be performed according to RECIST 1.1 after 6 weeks.
- o Brain CT/MRI scan (either, with contrast preferred) is required at Screening if not performed within the previous 6 weeks. Thereafter, brain CT/MRI scan should be done if clinically indicated by development of new specific symptoms. A bone scan should be done at Screening and beyond as clinically indicated. Bone metastases detected at Screening need to be followed at the subsequent tumor evaluation visits.
 - In order to mitigate potential infusion-related reactions, all subjects must receive premedication with an antihistamine and with paracetamol (acetaminophen) approximately 30 to 60 minutes prior to each dose of MSB0011359C (eg, 25-50 mg diphenhydramine and 500-650 mg paracetamol [acetaminophen] intravenous or oral equivalent) for the first 2 infusions. Premedication is optional and at the discretion of the Investigator after the second infusion. If Grade 2 infusion reactions are seen during the first two infusions, then premedication should not be stopped. Steroids as premedication are not permitted. MSB0011359C should be administered at the cohort prescribed dose by intravenous infusion over 1 hour (-10 minutes/+20 minutes, ie, over 50 to 80 minutes). The first 2 doses of MSB0011359C for any subject will be accompanied by overnight evaluation of at least 24 hours in an in-patient setting.
- r In-patient admission with periodic ECG and vital sign monitoring for a minimum of 24 hours. After 24 hours, investigator will decide the discharge of the subject based on the monitoring results and the results of in-person examination.
- s The observation period for DLTs refers to the first 21 days of IMP treatment in the dose escalation part for all subjects with data used for implementing the dose-escalation algorithm for determination of the MTD.

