- t At each visit, eye signs and symptoms should be checked. If clinically relevant findings, then an appropriate ophthalmology examination including slit lamp evaluation inclusive of the anterior segment and with visual acuity should be obtained within 2 days.
- u After 6 months, this will be assessed every 12 weeks and after a year, this will be assessed every 6 months.
- v Tumor evaluation will be assessed every 12 weeks after 12 months.
- w See Section 7.4.1.3 for definition of the AE reporting period and Section 7.4.1.6 for monitoring of subjects with AEs.
- x After Day 1, the physical examination will be a directed physical examination indicated by subject's symptoms.

Table 2	Schedule	of A	Asses	ssme	ents:	Exp	ansic	on Pa	ırt					Γ		
	Screening Assessments								ent Part days) ^a	:				Discontinuation/ End-of-Treatment Visits w	Safety Follow-up Visit ^w	Long-Term Follow-up ^b
		V1x V2 V3 V4 V5 V6 V7 V7 V8 V9 V10														
	W1 W1 W2 W3 W4 W5 W7 W7 W9 W11 W13								Up to 7/28 Days (+/- 5 days) after	10 Weeks						
Measure	Day -28 to First Treatment	D1	D2 ^{cc}	D8cc	D15	D22 ^{cc}	D29	D43	D43- 50 ^{cc}	D57	D71	D85	Until Progression	Decision of Discontinuation/ Last Treatment ^{c, d}	(+/- 2 weeks) after Last Treatment	Every 12 weeks (+/- 2 weeks)
Written informed consent	X															
Inclusion/exclusion criteria	X	X														
Medical history	X															
Cancer disease history	X															
Prior anticancer drug/ radiotherapy/procedures	X															
Other prior medications	X															
Demographic data	X															
HBV, HCV, and HIV testing	X															
Ophthalmology examination including slit lamp evaluation inclusive of the anterior segment and with visual acuity	X															
Physical examination s,u	X	X	X	X	X	X	X	X		X	X	X	6-weekly ^t	x/X	X	
Dermatological assessment ^e	X				X		X	X		X	X	X	6-weekly up to/including Week 25, then every 12 weeks	x/X	X	
SpO ₂	X	X			X		X	X		X	X	X	2-weekly	X	X	

Table 2	Schedule	of A	Asses	ssme	nts:	Exp	ansio	n Pa	ırt						T	
	Screening Assessments								ent Part days) ^a					Discontinuation/ End-of-Treatment Visits w	Safety Follow-up Visit ^w	Long-Term Follow-up ^b
		V1x	V2	V3	V4	V5										
									Up to 7/28 Days (+/- 5 days) after	10 Weeks						
Measure	Day -28 to First Treatment	D1	D2 ^{cc}	D8cc	D15	D22cc	D29	D43	D43- 50 ^{cc}	D57	D71	D85	Until Progression	Decision of Discontinuation/ Last Treatment ^{c, d}	(+/- 2 weeks) after Last Treatment	Every 12 weeks (+/- 2 weeks)

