- Number and percentage of participants with confirmed and unconfirmed ORR with a twosided 95% CI
- Number and percentage of participants with confirmed and unconfirmed DCR with a twosided 95% CI
- Spider graph of individual percentage of change in the sum of diameter since baseline
- Waterfall graph of the change in the sum of diameters between baseline and the best post-baseline assessment (i.e. minimum change since baseline)

Listing of tumor assessment: participant identifier, age, sex, MSI status, PD-L1 expression, date of death when death occurs, unconfirmed and confirmed BOR, visit, date(s) of imaging, description of target lesions (size, site, type, method, response), non-target lesions (status, site, type, method, response), and new lesions (site, type, method), sum of lesion diameters, percent change in target lesions at baseline, and overall response, sorted by dose level/cohort, participant identifier, and visit.

In addition, a listing presenting responses (CR, PR) occurring after a first progression will also be provided including: participant identifier, age, sex, MSI status, PD-L1 expression, date of start of subsequent therapy, unconfirmed and confirmed BOR, visit, date(s) of imaging, sum of lesion

diameters, percent change in target lesions from baseline, overall response and flag for response after progression, sorted by dose level/cohort, participant identifier, and visit.

When BOR as adjudicated by IRC and investigator assessment are both available, a listing of inconsistencies will be provided.

Listings of efficacy assessments for both Investigator and IRC assessment will also be provided including: cohort, participant identifier, age, sex, MSI status, PD-L1 expression, date of first study treatment, treatment duration, cBOR, PFS, time to response, DR and OS. Efficacy assessments will be given for both investigator and IRC. Subjects with treatment ongoing or response ongoing will be flagged.

14.2 **Duration of Response**

Duration of Response (DR) measured from the time measurement criteria are first met for CR/PR until the first date of PD or death due to any cause within 84 days (12 weeks) or last tumor assessment if death occurred during the treatment period, or within 168 days (24 weeks) of last tumor assessment if death occurred during the follow-up period.

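### PFS and DR censoring: the SAP's fixed 84-day on-treatment limit is one scan interval, not two, for escalation subjects treated past month 12; separately, PFS Table 3 leaves out non-CR/non-PD

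*SAP*

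**What the plan says.** - **Missed scans.** In SAP 14.2 (DR) and 14.3 (PFS), an event that follows two or more missing assessments is censored at the last evaluable scan. Both sections explain the limit with the same note: "2 times the scheduled time interval means 84 days during the treatment period and 168 days during the follow-up period".
- **Deaths.** PFS counts "death due to any cause within 84 days (12 weeks) of last tumor assessment if death occurred during the treatment period"; in follow-up the limit is 168 days. DR has the same limits, with a slip in the wording: "within 84 days (12 weeks) or last tumor assessment if death occurred during the treatment period".
- **PFS Table 3.** A PD or death is an event if it falls "Within two subsequent scheduled tumor assessments after last response assessment of CR, PR or SD". Otherwise, and for event-free subjects, the censoring date is the last scan rated CR, PR or SD, or first dose if that is later.
- **Scan schedule, escalation.** In Protocol Table 1 the row "Tumor evaluation/ staging (CT Scan/MRI/ other) ^{b, n, o, v" is 6-weekly until progression and carries footnote v: "Tumor evaluation will be assessed every 12 weeks after 12 months". Footnote n adds: "The subsequent tumor evaluations have a time window of 5 days prior to dosing (-5 days". Protocol 7.1.2.1 gives 6-weekly scans without the change at 12 months, but refers to Table 1 for the detailed schedule. Protocol 5.1.1.1 allows treatment past 12 months.
- **IRC outcomes.** SAP 14.1.2 makes non-CR/non-PD a valid IRC result when the IRC finds no measurable lesion at screening. It also provides for No Disease.

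**The concern.** The rule is stated as a principle (two scheduled intervals) and then frozen as a day count that fits only the 6-weekly phase. Once escalation scans become 12-weekly, the day count no longer carries out the principle. A progression or death that should count is then censored at the previous scan. SAP 14.2 and 14.3 report DR and PFS rates at 18, 24, 36 and 48 months, which is where this would show. In PFS, the note and Table 3 give different answers for the same subject.

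Table 3 has a second, unrelated gap. The text of 14.3 censors at the last evaluable scan, meaning any result that is neither missing nor NE. The table accepts only CR, PR or SD.

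**Working it through.** **1. The SAP's own figures.** Limit = 2 × interval in weeks × 7. On treatment, 6-weekly: 2 × 6 × 7 = 84 days. Follow-up, 12-weekly: 2 × 12 × 7 = 168 days. Both reproduce.

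**2. Escalation, on treatment after month 12.** The interval is 12 × 7 = 84 days, so the SAP limit is 84/84 = 1.0 interval. Two intervals are 168 days. If the change of schedule falls between the two scans, they are 42 + 84 = 126 days.

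**3. Events affected.** Each of these is past 84 days but within two scheduled assessments:
- a PD after one missed 12-weekly scan (nominal gap 168 days);
- a PD on the next scheduled scan, none missed, if window shifts push the gap past 84 days. The −5 day window gives gaps of 84 ± 5 = 79 to 89 days. If dosing visits also move by −3/+1 days (Table 1, footnote a), scans fall −8 to +1 days from nominal and gaps run 84 ± 9 = 75 to 93 days;
- an on-treatment death 85 to 168 days after the last scan.

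**4. Effect on the curve (constructed examples).** Scans fall on days 421, 505 and 589, 84 days apart. By the SAP 9.5 conversion, month 18 is 547.9 days and month 24 is 730.5 days.

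*Six subjects.* PDs on days 43, 43, 85 and 127; one subject event-free to day 1200; one with last scan on day 421, day 505 missed and PD on day 589 (gap 589 − 421 = 168).
- 84-day note: the last subject is censored at 421. Month-24 PFS = 2/6 = 33.3%.
- Table 3: PD at 589 with two at risk. Month-24 PFS = 2/6 × 1/2 = 16.7%.
- Month 18 is 33.3% under both.

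*Three subjects.* PD on day 43; PD on day 505 after a scan on day 421 (gap 84, counted); and one with last scan on day 421, day 505 missed and PD on day 589.
- 84-day note: the third subject leaves at 421, so the second is alone at risk on day 505. Month-18 PFS = 2/3 × 0 = 0%.
- Table 3: two are at risk on day 505. Month-18 PFS = 2/3 × 1/2 = 33.3%.

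The note removes an event but also shrinks the risk set, so the estimate can rise or fall.

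**5. Windows elsewhere.** One missed 6-weekly scan gives a nominal gap of 84 days, or 79 to 89 with the −5 day window. One missed follow-up scan, with ±2 weeks on each scan, gives 168 ± 28 = 140 to 196 days. A fixed day count can therefore censor a PD after only one missed scan in any cohort and period.

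**6. Table 3 and non-CR/non-PD.** Take an IRC subject with non-CR/non-PD at 42, 84, 126 and 168 days after first dose, then PD at 210 days.
- Text of 14.3: gap 210 − 168 = 42 days, so an event at (210 + 1)/30.4375 = 6.9 months.
- Table 3 read literally: no CR, PR or SD exists, and 210 days is beyond two scheduled assessments from first dose (84 days). The subject is censored at first dose, 1/30.4375 = 0.03 months.

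An event-free subject of this kind is also censored at first dose. With four other subjects progressing on days 100, 200, 300 and 400, PFS after day 200 is 3/5 = 60% if the fifth is kept and 2/4 = 50% if censored at first dose.

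**The case against.** The strongest case is that this may have touched nobody:
- Protocol 7.1.2.1 gives 6-weekly scans throughout. If sites followed that, 84 days was right. This stands as an uncertainty, but 7.1.2.1 defers to Table 1, which carries footnote v.
- Subjects who stop at 12 months enter follow-up, where 168 days is correct. This stands.
- Protocol 8.3.2 makes PFS and DR endpoints for expansion only; escalation gets them from SAP Table 2. Escalation scans are read locally, so these results are investigator-assessed, and the remark under that table warns that some investigator endpoints may only be listed or plotted. However, 14.2 and 14.3 do plan investigator analyses.
- No tests are performed (SAP 9.10), the CSR and addendum are approved, and no final analysis follows (SAP 6.1). This limits the consequence but does not remove the inconsistency.

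Four stronger readings are tempting and are not supported:
- *Late PFS and DR are biased upward.* The three-subject example goes the other way.
- *The 12-weekly change also affects GC, ESCC and BTC.* The tumor row in Protocol Table 2 is redacted, and 7.1.2.2 says 6-weekly. The documents do not show it.
- *DR has two competing rules.* Table 3 is for PFS only. DR has one numeric limit, which is out of date after month 12.
- *The number of affected subjects can be estimated.* The documents give no late PFS, continuation or missed-scan rates. SAP 16.1.1 speaks of a low number still on treatment at the onset of COVID-19, and the last participant started in August 2017. This suggests some long treatment, but the cohort is not stated.

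**Conclusion.** Both faults hold as written, and both are minor. The 84-day limit is half of what the SAP's own definition requires for escalation subjects treated past month 12, if Table 1 footnote v governs the schedule. Reach is at most the 18 planned escalation subjects, in dose levels of 3 to 6, reported descriptively. It is nil if none was treated past month 12. Where one event is affected, a dose-level estimate can shift by tens of percentage points in either direction.

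The Table 3 gap concerns IRC-assessed PFS only. It can misdate an event-free subject or drop a real progression. Measurable disease is an entry criterion for expansion, so such subjects should be few; the documents give no count. Table 3 does not cover No Disease either.

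**What to change.** 1. In SAP 14.2 and 14.3, including the death limits, replace the fixed day counts by two scheduled assessments under the schedule in force: nominally 84, 126 or 168 days. State that a scan within its protocol window counts as on schedule. In the DR death text, change the "or" before the last tumor assessment to "of".
2. In Table 3, replace the CR, PR or SD anchor by the last evaluable assessment (not missing, not NE). Alternatively, add non-CR/non-PD and state how No Disease is handled.
3. Reconcile Protocol 7.1.2.1 with Table 1 footnote v.
4. From the PFS and tumor-assessment listings, in all cohorts, count subjects whose event status or date changes. The DR listing has no last-scan date, so DR needs the tumor-assessment listing. If any subject changes, report a correction or sensitivity table; if none, say so.

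The cost is SAP wording and one listing check. The window allowance could also change some first-year or follow-up censoring in GC, ESCC and BTC; the same check would show it.

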7.2.5 Computed Tomography or Magnetic Resonance Imaging Scans for Tumor Assessment at Baseline

A CT scan or MRI (if MRI is used, CT of chest is mandatory) of the chest, abdomen, and pelvis (at a minimum and other established assessments of tumor burden if CT/MRI imaging is not sufficient for the individual subject; other regions as specifically required for specific tumor indications) will be performed within 28 days prior to trial treatment start in order to document the baseline status of the tumor disease using RECIST 1.1 target and nontarget lesions and secondarily using mRECIST for subjects in the HCC cohort (see vendor manual). However, if the results of a CT scan or MRI performed within 4 weeks prior to first treatment are available, the Screening CT/MRI does not need to be performed.

A brain CT/MRI scan (either, contrast preferred) is required at Screening if not performed within the previous 6 weeks. Thereafter, brain CT/MRI scan should be done if clinically indicated by development of new specific symptoms.

A bone scan should be done at Screening as clinically indicated.

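### SAP 14.3 Table 3, read literally, censors at first dose anyone whose PD or death precedes a CR, PR or SD assessment, contradicting the section's own PFS definition and bullets

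*SAP*

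**What the plan says.** SAP 14.3 treats PFS events in three places.

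- **Definition.** PFS runs from first administration "until the first date of PD or death due to any cause within 84 days (12 weeks) of last tumor assessment" for a death on treatment; for a death in follow-up the limit is 168 days. PD carries no condition on what came before it.
- **Bullets.** A subject with no baseline or no post-baseline tumor assessment is "censored on the date of first dose unless death occurred on or before the time of the second planned tumor assessment"; such a death counts as an event. Another bullet censors events that follow two or more missed assessments. No bullet censors PD found on the first scan.
- **Table 3.** The text announces that "PFS event / censoring are defined in Table 3". The event row covers a subject who progressed or died "Within two subsequent scheduled tumor assessments after last response assessment of CR, PR or SD". The remaining rows censor at "Date of last tumor assessment with outcome CR, PR or SD or date of first dose, whatever is later".

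Protocol 8.5.3.1 counts the first IRC-read radiological PD or death from any cause, sets no condition of an earlier CR, PR or SD, and leaves the censoring rules to the SAP. The SAP does not say whether text or table prevails.

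**The concern.** Table 3 is presented as the definition, so a programmer could reasonably work from it alone. Its event row has a reference point only for subjects who have had a CR, PR or SD assessment. The others fall into the censored row and, having no such date, are censored on Day 1.

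These subjects are not a curiosity. SAP 14.1.1 and 14.1.2 have a best-response category for progression within 12 weeks that does not qualify for CR, PR or SD, and SAP 14.1 expects some patients to have no on-treatment scan because of early progression. Dropping them from the risk set at Day 1 raises the rest of the PFS curve. It could also distort the subgroup curves planned in SAP 14.5 (PD-L1, BTC classification, ADA, nAb) if early progression differs between groups.

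Table 3 also omits the non-CR/non-PD rating that SAP 14.1.2 allows for the IRC. A subject with only that rating would be censored at first dose, whereas the bullets would use the last evaluable scan.

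**Working it through.** **1. The plan's own windows.** Scans are at Week 7 and then every 6 weeks (protocol 7.1.2.2), and every 12 weeks in follow-up (protocol 7.1.5.2).

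- On treatment: 2 × 6 × 7 = 84 days. Follow-up: 2 × 12 × 7 = 168 days. Both match SAP 14.3.
- First planned scan: Day 1 + 42 = Day 43. Second: Day 1 + 84 = Day 85.

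**2. Where the limits end if they run from the baseline scan.** That scan "will be performed within 28 days prior to trial treatment start". If it is taken s days before Day 1, the on-treatment limit is Day 85 - s and the follow-up limit is Day 169 - s.

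| s | On treatment | Follow-up |
|---|---|---|
| 28 | Day 57 | Day 141 |
| 14 | Day 71 | Day 155 |
| 0 | Day 85 | Day 169 |

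**3. Four subjects under the three statements.** The definition column assumes, for deaths, that the limits run from the baseline scan.

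| Subject | Definition | Bullets | Table 3, literal |
|---|---|---|---|
| PD on first scan, Day 43 | Event | Event | Censored Day 1 |
| On-treatment death Day 30, no post-baseline scan | Event | Event | Censored Day 1 |
| On-treatment death Day 70, no post-baseline scan, s = 28 | Not an event (limit Day 57) | Event | Censored Day 1 |
| Follow-up death Day 100, no post-baseline scan | Event (limit Day 141 to 169) | Censored at first dose | Censored Day 1 |

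The first two rows are a conflict between Table 3 and everything else. Definition and bullets differ only in the last two.

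**4. Effect on the curve.** Let f be the share of subjects with PD or death before any CR, PR or SD assessment, and P the product of the later Kaplan-Meier factors. If these events all precede anyone else's event or censoring:

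- counted as events: S(t) = (1 - f) × P
- censored at Day 1: S(t) = P
- ratio: 1/(1 - f)

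| f (assumed) | 10% | 20% | 30% | 40% | 50% |
|---|---|---|---|---|---|
| Factor | 1.11 | 1.25 | 1.43 | 1.67 | 2.00 |

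**5. Illustration.** N = 30, with about 25% of those remaining (rounded to whole subjects) assumed to have an event at each scan from Day 85.

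| f | 6-month PFS, events counted | 6-month PFS, Table 3 literal | Median, months | Events |
|---|---|---|---|---|
| 20% | 10/30 = 33.3% | 10/24 = 41.7% | 4.2 vs 5.6 | 30 vs 24 |
| 40% | 8/30 = 26.7% | 8/18 = 44.4% | 2.8 vs 5.6 | 30 vs 18 |

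**The case against.** The literal reading may not be what was meant. Table 3's censoring cells already name first dose as the fallback. Carried into the event row, two 6-week intervals from first dose end on Day 85, which agrees with the last bullet. That is a plausible intention, but the event row does not state it.

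A reader might infer that the section gives three incompatible rules for everyone who progresses or dies early. It does not. For first-scan PD, definition and bullets agree and only Table 3 differs. For deaths without a post-baseline scan, the last bullet reads naturally as a specific exception to the general definition, and the text never says that the 84/168-day clock starts at the baseline scan.

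A reader might also infer that the reported PFS is inflated. The documents do not show which rule was programmed, and they give no value for f. Deaths with no scan are limited by the required life expectancy of at least 12 weeks (protocol 5.3.1) and by the End-of-Treatment tumor evaluation when no PD has been documented (protocol 7.1.4.2). If f were only 5% to 15%, a true rate of 20% would read 21.1% (0.20/0.95) to 23.5% (0.20/0.85). That is small beside a rough 95% half-width of 1.96 × √(0.2 × 0.8/30) = 14 points at n = 30. These limits do not apply to first-scan PD, however, and the error runs in one direction only.

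Finally, PFS is descriptive and untested (SAP 9.10), the cohorts are hypothesis-generating (protocol synopsis), and the BTC interim uses BOR (protocol 8.6). The CSR and addendum are approved and the final analysis is cancelled (SAP 6.1). This lowers the severity. It does not remove the point, because SAP 4 allows these analyses to go into submissions or manuscripts.

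**Conclusion.** Table 3 as written contradicts the definition and bullets of its own section, and protocol 8.5.3.1, for subjects whose PD or death precedes any CR, PR or SD assessment. That much rests on the text alone. The overstatement is conditional on literal programming of Table 3. If that happened, its direction is certain for any f above zero and its size is 1/(1-f) at later times, under the ordering assumption in step 4 of the working. The 10% to 50% range for f and the later event pattern are assumptions, so the actual size is unknown. The choice between the Day 85 bullet and limits run from the baseline scan is a lesser ambiguity affecting a narrow group of deaths. Should-fix: a secondary, descriptive endpoint with a cheap remedy.

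**What to change.** 1. **Event row of Table 3:** *within two scheduled assessment intervals after the last evaluable tumor assessment before the PD or death, or after first dose if there is no evaluable post-baseline assessment before it*. The words *before the PD or death* are needed: a PD scan is itself evaluable, and without them the window could start at that scan and defeat the missed-assessment rule.
2. **Both censoring-date cells:** replace the CR/PR/SD condition with *last evaluable (not missing, not NE) tumor assessment before the event or censoring*, keeping first dose as the fallback. This also covers non-CR/non-PD.
3. **One added sentence:** for subjects with no post-baseline assessment the last bullet governs (death on or before the second planned assessment is an event), and the 84/168-day limits do not run from the baseline scan.
4. **Check:** the sponsor confirms which rule was programmed for the CSR and the addendum. The PFS listing in SAP 14.3 already carries the event or censoring reason per participant. If Table 3 was applied literally, correct the PFS rates, medians and subgroup curves.

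The cost is a few lines of SAP text and one derivation check. Outputs need re-running only if the literal rule was used, in which case reported PFS would become less favourable.
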